### **8.1.2 Safety Analyses**

The All-Subjects-as-Treated population will be employed for safety analyses.

### **8.1.3 Power and Sample Size**

The calculation of power and sample size for each cohort does not account for interim analysis. Cohort A (triple negative breast cancer subjects): With approximately 26 evaluable PD-L1 positive subjects with triple negative breast cancer, the study has approximately 80% power to detect a 25% difference in ORR under the null hypothesis of ORR=20% with a type I error rate of 2.5% if the true ORR is 45%. Success for this hypothesis requires at least 10/26 responses. The actual number of subjects enrolled may be larger than 26 to ensure that at least 26 subjects are evaluable for analysis.

Cohort B (head and neck cancer subjects): HPV negative head and neck cancer subjects will be evaluated separately from HPV positive head and neck cancer subjects. With a maximum of 22 evaluable PD-L1 positive subjects with HPV negative head and neck cancer, the study has approximately 80% power to detect a 25% difference in ORR under the null hypothesis of ORR=10% with a type I error rate of 2.5% if the true ORR is 35%. Success for this hypothesis requires at least 6/22 responses. The actual number of subjects enrolled may be larger than 22 to ensure that at least 22 subjects are evaluable for analysis.

With a maximum of 12 evaluable PD-L1 positive subjects with HPV positive head and neck cancer, the study has approximately 73% power to detect a 35% difference in ORR under the null ORR=20% with a type I error rate of 5% if the true ORR is 55%. Success for this hypothesis requires at least 6 responses. The actual number of subjects enrolled may be larger than 12 to ensure that at least 12 subjects are evaluable for analysis. However, if 6 responses are observed prior to 12 subjects with HPV positive head and neck cancer enrolling in the trial, enrollment may be stopped in this group as the hypothesis success criterion will have been reached.

Cohort C (urothelial tract cancer subjects): With a maximum of 22 evaluable PD-L1 positive subjects with urothelial tract cancer, the study has approximately 80% power to detect a 25% difference in ORR under the null hypothesis of ORR=10% with a type I error rate of 2.5% if the true ORR is 35%. Success for this hypothesis requires at least 6/22 responses. The actual number of subjects enrolled may be larger than 22 to ensure that at least 22 subjects are evaluable for analysis.

Cohort D (gastric cancer subjects): With a maximum of 32 evaluable PD-L1 positive subjects with gastric cancer, stratified to include 16 Asia Pacific (AP) and 16 non-AP, the study has approximately 90% power to detect a 25% difference in ORR under the null hypothesis of ORR=15% with a type I error rate of 2.5% if the true ORR is 40%. Success for this hypothesis requires at least 10/32 responses. A total of 16 AP subjects will provide approximately 80% power with a type I error rate of 0.1 to detect a 25% difference in ORR under the null hypothesis of ORR=15% if the true ORR is 40%. At least 4/16 responses will be needed to claim the success of this hypothesis for AP population. The actual number of subjects enrolled may be larger than 32 to ensure that at least 32 subjects are evaluable for analysis.

Cohort B2 (head and neck cancer subjects, expansion cohort): With 100 evaluable subjects in Cohort B2, the study provides >99% power to detect a 15% difference in ORR under the null hypothesis of ORR=5% with a type I error rate of 2.5% if the true ORR is 20%. Success for this hypothesis requires at least 11/100 responses. The actual number of subjects enrolled may be larger than 100 to ensure at least 100 subjects are evaluable for analysis.

Cohorts B and B2 previously treated with cetuximab and platinum: With 60 evaluable head and neck cancer subjects previously treated with cetuximab and platinum, the study has 93% power to detect a 15% difference in ORR under the null hypothesis of ORR=5% with a type I error rate of 2.5% if the true ORR is 20%. Success for this hypothesis requires at least 8/60 responses.

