In subjects who have initial evidence of radiological PD, it is at the discretion of the treating physician whether to continue a subject on study treatment until repeat imaging is obtained a minimum of 4 weeks later. This decision should be based on the clinical judgment of the subject's overall clinical condition, including performance status, clinical symptoms, and laboratory data. Subjects may receive treatment while waiting for confirmation of PD if they are clinically stable as defined by the following criteria:

- Absence of signs and symptoms indicating disease progression
- No decline in ECOG performance status
- Absence of rapid progression of disease
- Absence of progressive tumor at critical anatomical sites (e.g., cord compression) requiring urgent alternative medical intervention

When feasible, subjects should not be discontinued until progression is confirmed. This allowance to continue treatment despite initial radiologic progression takes into account the observation that some subjects can have a transient tumor flare in the first few months after the start of immunotherapy, but with subsequent disease response. Subjects that are deemed clinically unstable are not required to have repeat imaging for confirmation of progressive disease. Retrospective independent central radiology review of all imaging time points will be performed for this study using RECIST 1.1 and volumetric analysis. Additional information is included in the Site Imaging Manual.

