### 8.2.5.1 Statistical Methods for Efficacy Analyses

Efficacy will be evaluated separately in each cohort. For the primary efficacy endpoint independent centrally reviewed RECIST 1.1 response rate, the point estimate, exact 95% Clopper-Pearson confidence interval, and p-value for testing the RECIST 1.1 response rate is greater than the historical control for each cohort will be provided using exact binomial distribution. Subjects in the primary analysis population (FAS) without response data will be counted as non-responder.

Secondary efficacy evaluations of RECIST 1.1 response based on Investigator assessment will also be conducted using the same methodology as for the primary efficacy analysis. Efficacy for the secondary analysis of RECIST 1.1 response by independent central radiology review among subjects with HPV positive head and neck cancer will be evaluated in the same manner as in the primary analysis.

For PFS endpoint, Kaplan-Meier (KM) curves and median estimates from the KM curves will be provided as appropriate. Subjects without efficacy evaluation data or without survival data will be censored at Day 1. [Table 11](#) summarizes the key efficacy analyses.

Table 11 Analysis Strategy for Key Efficacy Variables

Endpoint/Variable ‡ (Description, Time Point)	Statistical Method	Analysis Population	Missing Data Approach
Overall RECIST 1.1 response rate based on independent central radiology review (Cohort A, Cohort B HPV negative subjects, Cohort C, and Cohort D evaluated separately)	Exact test of binomial parameter	FAS (Primary) ASaT (Supportive)	Subjects with missing data are considered non-responders
Overall RECIST 1.1 response rate based on independent central radiology review for subjects in Cohort B2	Exact test of binomial parameter	FAS (Primary) ASaT (Supportive)	Subjects with missing data are considered non-responders
Overall RECIST1.1 response rate based on independent central radiology review, Cohort B HPV positive subjects,	Exact test of binomial parameter	FAS (Primary) ASaT (Supportive)	Subjects with missing data are considered non-responders
Overall RECIST 1.1 response rate based on independent central radiology review, Cohort D AP subjects.	Exact test of binomial parameter	FAS (Primary) ASaT (Supportive)	Subjects with missing data are considered non-responders

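### HPV-positive enrolment may close at six responses of unstated source, although success is judged by retrospective central review, so the group can end short of its own criterion

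*Combined protocol and SAP*

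**What the plan says.** Section 8.1.3, repeated in 8.2.7, caps the HPV-positive group of Cohort B at 12 evaluable subjects. For that number it states that "the study has approximately 73% power to detect a 35% difference in ORR", from a null rate of 20% to a true rate of 55%, at a 5% type I error. The success rule reads: "Success for this hypothesis requires at least 6 responses". If 6 responses are seen before 12 such subjects have enrolled, "enrollment may be stopped in this group as the hypothesis success criterion will have been reached". The clause does not say who reads those responses or whether they must be confirmed.

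Other sections say how the hypothesis is judged:

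- Section 3.2, secondary objective 1, sets the response rate on independent central radiology review.
- Section 8.2.5.1 says that central response "among subjects with HPV positive head and neck cancer will be evaluated in the same manner as in the primary analysis". That means a point estimate, a Clopper-Pearson interval and an exact binomial p-value.
- Section 4.2.3.1 gives the timing: "Retrospective independent central radiology review of all imaging time points will be performed for this study". The flow-chart notes and section 7.1.2.5.1 assign subject management to the local reading.
- Section 7.1.2.5.3 asks for confirmation of response by a scan at least 4 weeks later.
- Section 8.2.4.1 admits to the FAS only subjects whose measurable baseline disease is established by central review.
- Section 8.1.4 states that this group has no interim analysis.

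**The concern.** The clause justifies closing enrolment by treating the criterion as already met. The criterion belongs to the central read, and the plan schedules no central read at that moment. The responses visible in real time are the sites' own.

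Stopping at exactly six leaves no margin. One response not upheld centrally, one not confirmed, or one responder excluded from the FAS for lack of centrally measurable disease brings the count below six. Enrolment may by then have closed with fewer than 12 subjects. What is at stake is the power of this secondary hypothesis, which was calculated for 12 subjects.

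A smaller matter follows from the same clause. The sample shortens only when results are good, so the simple proportion of responders leans upward.

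**Working it through.** **Inputs from the plan (8.1.3, 8.2.7):** maximum n = 12, null 0.20, alternative 0.55, cut-off 6, stated power about 73%, nominal type I error 5%.

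**Step 1. Reproduce the plan's figure.** With X binomial(12, p):

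- P(X ≥ 6 | p = 0.55) = 0.739, which agrees with about 73%.
- P(X ≥ 6 | p = 0.20) = 0.0194.
- A cut-off of 5 would give 0.0726, so 6 is the smallest cut-off within 5%.

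**Step 2. One assessor throughout.** Reaching 6 responses by the 12th subject is the same event as having at least 6 of 12. An early stop on central responses therefore leaves power at 0.739 and type I error at 0.0194.

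**Step 3. Stop on site reads, success on central reads.** The documents give no agreement rate and no accrual rate, so these are assumptions: each site response is upheld centrally with probability c between 0.80 and 0.95, there are no central-only responders, and the true central rate is 0.55. The site rate is then 0.55/c.

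With no enrolment lag, success needs 6 site responses within 12 subjects and all six upheld:

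P(success) = P(Bin(12, 0.55/c) ≥ 6) × c^6

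- c = 0.80: 0.952 × 0.262 = 0.25
- c = 0.90: 0.861 × 0.531 = 0.46
- c = 0.95: 0.802 × 0.735 = 0.59

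Given an early stop, the chance of ending with fewer than 6 central responses is 1 − c^6: 0.74, 0.47 and 0.26 respectively.

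**Step 4. Add enrolment lag.** Let L further subjects enrol before the sixth site response is known, with the total capped at 12. Simulation (400,000 trials per setting) gives the chance of at least 6 central responses:

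| L | c = 0.80 | c = 0.90 | c = 0.95 |
|---|---|---|---|
| 0 | 25% | 46% | 59% |
| 2 | 59% | 69% | 72% |
| 4 | 72% | 73% | 74% |
| No early stop | 74% | 74% | 74% |

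At L = 4 enrolment closes before 12 in 13–30% of trials, and 2–14% of those end short of 6.

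If central review also upgrades 10% of site non-responders, the zero-lag figures become 35% (c = 0.80) and 55% (c = 0.90).

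**Step 5. Count rule against exact p-value.** At the 20% null, 5 of 10 gives p = 0.033 and 5 of 11 gives p = 0.0504. A group that closes at 10 with 5 central responses fails the 6-response rule but passes an exact 5% test. On exact p < 0.05, zero-lag success is 65–73%.

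**Step 6. Type I error.** The central count at an early stop cannot exceed the count had all 12 been enrolled, so under the 6-response rule the error is at most 1.9%.

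**Step 7. Bias of responders/n.** One assessor, no lag, stop at the sixth response or at 12: the mean estimate is 0.525, 0.579 and 0.631 at true rates 0.50, 0.55 and 0.60, a bias of 2.5, 2.9 and 3.1 points. At 0.55 it falls to about 1.2 points at L = 2 and 0.3 at L = 4. Clopper-Pearson coverage at zero lag was at least 96% at every true rate checked from 0.2 to 0.7.

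**The case against.** The documents nowhere say that site reads trigger the stop. The clause gives the success criterion as its reason, and that criterion is central, so the six could be meant as central responses. Retrospective reading need not mean reading at study end. The plan also asks for confirmation generally, and where it wants unconfirmed responses counted (the interim rules for Cohorts A, B and C) it says so. This has force: the wording may only lack a qualifier. But nothing in the plan provides a central read in time for the decision, and 8.1.4 rules out an interim analysis here, so the justification is not secured.

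The timing objection is stronger. The first scheduled scan is at 8 weeks and confirmation takes at least 4 more, so zero lag is not a realistic norm. A reader might infer that power collapses to about 25%. The documents do not support that, because it requires immediate knowledge of every response, 80% agreement and no upgrades. With four subjects of lag the loss is at most about 2 points.

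A reader might also infer a false-positive problem, or that the estimate and interval need replacing. Neither follows. Type I error is not inflated and interval coverage holds. The estimator 5/(N − 1) is unbiased only if enrolment ends exactly at the sixth response and the stop is always used. The stop is optional and subjects may enrol past the sixth response, so that estimator should not be prescribed.

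Finally, the stakes are limited: this is a secondary hypothesis, and the 12 are already within the planned total (26 + 22 + 12 + 22 + 32 = 114). Sections 1.0 and 2.1 describe enrolment to Cohorts A–D as previously planned, so changing the rule may have little practical effect now.

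**Conclusion.** The point stands as a minor design weakness. The early-stop clause asserts that the criterion is met without requiring the read on which it is judged, so enrolment can close with fewer than 12 subjects and fewer than 6 central responses. A shortfall is possible, not certain, since the stop is optional and subjects already enrolled may still respond.

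The size of the loss rests on the assumed agreement and lag. It ranges from severe with no lag to negligible with a lag of four subjects. The documents do not say where in that range the trial would fall. The upward bias in the response rate is at most about 3 points and concerns estimation only. The plan also leaves open whether the 6-response count or the exact p-value governs when fewer than 12 are enrolled.

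**What to change.** In 8.1.3 and 8.2.7, replace the condition of six observed responses with: *if 6 confirmed responses by independent central radiology review are documented in FAS-evaluable subjects*. Otherwise continue to the planned 12. With that trigger the stated power and the 1.9% type I error are kept.

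If enrolment stops early, report that the sample size was data-dependent and that the simple response rate is biased upward by at most about 3 points (about 0.3 with a lag of four subjects). No replacement estimator or interval is needed.

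The cost is an earlier batch read by the existing central vendor, or enrolment of subjects already in the plan.

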#### **8.1.1 Efficacy Analyses**

The full analysis set (FAS) population (defined as all subjects with a baseline scan with measurable disease; by independent central radiology review for each cohort, and who either have a post baseline scan or discontinue the trial due to progressive disease or a drug-related AE) will serve as the primary population for the analyses of efficacy data in this trial. Supportive analyses of efficacy will be conducted in the all subjects as treated (ASaT) population and the FAS population by Investigator review. For each cohort, overall response rate will be used as the primary endpoint for efficacy assessment. A 95% confidence interval along with a one-sided p-value for testing the null hypothesis based on the binomial distribution will be provided for the response rate in each cohort. The respective cohort is considered to have reached the efficacy objective if the corresponding p-value for testing the respective null hypothesis is less than 2.5%. An outline of the efficacy analysis strategy is presented in [Table 9](#) below.

Table 9 Primary Analysis Strategy for Efficacy Endpoints

Endpoint/Variable‡ (Description, Time Point)	Statistical Method	Analysis Population	Missing Data Approach
Primary:			
Overall RECIST 1.1 response rate based on independent central radiology review (Cohort A, Cohort B HPV negative subjects, Cohort C, and Cohort D evaluated separately)	Exact test of binomial parameter	FAS	Subjects with missing data are considered non-responders
Overall RECIST 1.1 response rate based on independent central radiology review for subjects in Cohort B2	Exact test of binomial parameter	FAS	Subjects with missing data are considered non-responders
Secondary:			
Overall RECIST 1.1 response rate based on independent central radiology review, Cohort B HPV positive subjects,	Exact test of binomial parameter	FAS	Subjects with missing data are considered non-responders
Overall RECIST 1.1 response rate based on independent central radiology review, Cohort D AP subjects.	Exact test of binomial parameter	FAS	Subjects with missing data are considered non-responders
Overall RECIST 1.1 response rate based on based on independent central radiology review, for subjects previously treated with cetuximab and platinum in Cohorts B and B2	Exact test of binomial parameter	FAS	Subjects with missing data are considered non-responders

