Cohort C (urothelial tract cancer subjects): With a maximum of 22 evaluable PD-L1 positive subjects with urothelial tract cancer, the study has approximately 80% power to detect a 25% difference in ORR under the null hypothesis of ORR=10% with a type I error rate of 2.5% if the true ORR is 35%. The null hypothesis rate of 10% is based on the historic response rate of single agent pemetrexed (RR 6%) or vinflunine (RR 9%) chemotherapy for bladder cancer [39, 40]. Success for this hypothesis requires at least 6/22 responses. The actual number of subjects enrolled may be larger than 22 to ensure that at least 22 subjects are evaluable for analysis.

Cohort D (gastric cancer subjects): With a maximum of 32 evaluable PD-L1 positive subjects with gastric cancer, stratified to include 16 Asia Pacific (AP) and 16 non-AP, the study has approximately 90% power to detect a 25% difference in ORR under the null hypothesis of ORR=15% with a type I error rate of 2.5% if the true ORR is 40%. Success for this hypothesis requires at least 10/32 responses. A total of 16 AP subjects will provide approximately 80% power with type I error rate of 0.1 to detect a 25% difference in ORR under the null hypothesis of ORR=15% if the true ORR is 40%. At least 4/16 responses will

be needed to claim the success of this hypothesis for the AP population. The null hypothesis rate of 15% is based on the response rate in large ( $n > 100$ ), trials for standard of care chemotherapy irinotecan/mFOLFIRI (RR 12%), and irinotecan/docetaxel (RR 13%) for 2nd line metastatic gastric cancer [28, 29]. The actual number of subjects enrolled may be larger than 32 to ensure that at least 32 subjects are evaluable for analysis.

Cohort B2 (head and neck cancer subjects, expansion cohort): With 100 evaluable subjects in Cohort B2, the study provides >99% power to detect a 15% difference in ORR under the null hypothesis of ORR=5% with a type I error rate of 2.5% if the true ORR is 20%. Success for this hypothesis requires at least 11/100 responses. The null hypothesis rate of 5% is based on historic response of chemotherapy in head and neck cancer trials [37]. The actual number of subjects enrolled may be larger than 100 to ensure at least 100 subjects are evaluable for analysis.

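### The Asia Pacific gastric success rule (at least 4 of 16 responses) has a one-sided type I error of 21%, not the stated 10%; the stated error rate and power fit 5 of 16

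*Combined protocol and SAP*

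**What the plan says.** Section 8.1.3 (Cohort D) gives the design of the AP hypothesis: "A total of 16 AP subjects will provide approximately 80% power with a type I error rate of 0.1", for a null overall response rate (ORR) of 15% and a true ORR of 40%. The criterion follows: "At least 4/16 responses will be needed to claim the success of this hypothesis for AP population". Section 8.2.7 repeats the design ("A total of 16 AP subjects will provide approximately 80% power with type I error rate of 0.1") and the same 4/16 count, there described as what will "be needed to claim the success of this hypothesis for the AP population".

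The hypothesis is secondary hypothesis 2 in section 3.2. Tables 9 and 11 list the method for Cohort D AP subjects as "Exact test of binomial parameter". On sidedness, section 8.1.1 says that "a one-sided p-value for testing the null hypothesis based on the binomial distribution will be provided for the response rate in each cohort". Section 8.1.4 plans no efficacy interim analysis for Cohort D, so the rule is a single-stage one.

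**The concern.** The sample size, null rate, alternative, error rate, power and success count are all printed together, and they do not agree. A 15% null gives an expected count of 16 × 0.15 = 2.4 responses. Four is only 1.6 above that, which is little separation for a 10% error rate in so small a sample.

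At stake is a success claim for a named hypothesis in a regional population. If the printed count is used, the claim carries about twice the false-positive risk that the plan discloses. A result of exactly 4/16 would also leave the plan with two opposite answers, one from the count and one from the exact test at 0.1. That should be settled before the data are read.

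**Working it through.** **Inputs (sections 8.1.3 and 8.2.7).** n = 16; null rate p0 = 0.15; alternative p1 = 0.40; stated type I error 0.1; stated power about 80%; success if X ≥ 4. The test is exact binomial (Tables 9 and 11) and one-sided (section 8.1.1).

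**Formula.** For a rule that claims success when X ≥ r, type I error = P(X ≥ r | 16, p0) and power = P(X ≥ r | 16, p1), with X binomial.

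**The plan's figures at r = 4.**

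- Under 15%, the probabilities of 0, 1, 2 and 3 responses are 0.0743, 0.2097, 0.2775 and 0.2285. Before rounding they sum to 0.7899. Type I error = 1 − 0.7899 = 0.2101.
- Under 40%, the same four probabilities are 0.0003, 0.0030, 0.0150 and 0.0468, summing to 0.0651. Power = 1 − 0.0651 = 0.9349.

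Neither stated figure is reproduced.

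**Neighbouring counts.**

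| Success if at least | Type I error at 15% | Power at 40% |
|---|---|---|
| 3/16 | 0.439 | 0.982 |
| 4/16 (as printed) | 0.210 | 0.935 |
| 5/16 | 0.079 | 0.833 |
| 6/16 | 0.024 | 0.671 |

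Five is the smallest count with type I error at or below 0.1, and its power is close to the stated 80%.

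**Other ways the 4/16 rule might have been obtained.** None brings it to 0.10:

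- Normal approximation: 0.131 without continuity correction, 0.221 with it.
- Mid-p: 0.145. Wald: 0.178.
- The normal-approximation critical value at one-sided 0.10 is 4.23, which again means 5 responses.
- Reading 0.1 as two-sided (0.05 per side) would require 6/16.
- The 4/16 rule meets 0.10 only with a null rate of about 11% or lower (0.091 at 11%, 0.116 at 12%). The plan states 15% and supports it with trial rates of 12% and 13%.

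**Control: the plan's other single-arm rules.** Each is the smallest count that keeps the exact type I error within its stated level.

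| Rule | Null | Stated level | Exact type I error | With one response fewer |
|---|---|---|---|---|
| 10/26 (A) | 20% | 0.025 | 0.023 | 0.059 |
| 6/22 (B HPV negative; C) | 10% | 0.025 | 0.018 | 0.062 |
| 6/12 (B HPV positive) | 20% | 0.05 | 0.019 | 0.073 |
| 10/32 (D) | 15% | 0.025 | 0.016 | 0.041 |
| 11/100 (B2) | 5% | 0.025 | 0.011 | 0.028 |
| 8/60 (prior cetuximab and platinum) | 5% | 0.025 | 0.010 | 0.030 |

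The AP rule is the only one that exceeds its stated level. The convention the others follow gives 5/16.

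**If more than 16 AP subjects are evaluable.** The plan allows Cohort D to exceed 32. A fixed count of 4 then has type I error 0.244 at n = 17 and 0.280 at n = 18. A fixed count of 5 has 0.099 at 17 and 0.121 at 18.

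**The case against.** The arithmetic is not in dispute. The case for treating the point as minor runs as follows.

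- **It is a secondary hypothesis.** The AP response rate is not among the key secondary endpoints in section 8.2.3.1 and has no place in the error control of section 8.2.6. Section 8.2.5 allows nominal p-values for other efficacy analyses, and the footnote to Table 9 leaves AP analyses to be done as appropriate. No enrolment or stopping decision is tied to the count, and the Cohort D primary rule (10/32) is sound. All of this stands and limits the consequences. But the plan still names the hypothesis, states an error rate and gives a count for claiming success, so the three should agree.
- **The 21% applies at a true rate of exactly 15%.** That is a chemotherapy control rate, not an absence of activity. The chance of success under the 4/16 rule is 0.116 at 12%, 0.068 at 10% and 0.007 at 5%. This is correct. Type I error is nevertheless defined at the stated null, and that is the figure the plan gives as 0.1.
- **Tables 9 and 11 give no significance level.** The 0.1 appears only in the sample-size text, and section 8.2.5 defaults to two-sided 0.05 unless otherwise stated. The conflict at 4/16 therefore relies on reading the 0.1 as the level for this test. A stricter level would widen the conflict, since p = 0.21 fails at either.
- **The confidence interval does not separate the two counts.** The exact 95% interval is 7.3% to 52.4% for 4/16 and 11.0% to 58.7% for 5/16. Both include 15%, so the interval is no argument for either.
- **The documents do not say which figure is wrong.** That the count is one too low is an inference. It rests on both stated properties fitting 5/16 and on the pattern of the other rules.

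**Conclusion.** The point holds. As printed, the AP rule has an exact one-sided type I error of 0.210 against a stated 0.1, and power of 0.935 against a stated value of about 80%. A drug whose true response rate in AP subjects equals the 15% historical control would meet the criterion about one time in five. The stated properties belong to 5/16 (0.079 and 0.833).

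This assumes 16 evaluable AP subjects, a single analysis, independent responses and a one-sided test. The AP sentence does not state sidedness; a two-sided reading makes the mismatch larger. The error is confined to this secondary hypothesis and does not affect the Cohort D primary conclusion.

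**What to change.** In sections 8.1.3 and 8.2.7, change the AP criterion from 4/16 to 5/16 and give its exact properties: one-sided type I error 0.079, power 0.833 at a true ORR of 40%. State in Tables 9 and 11 that this test is one-sided at 0.1. Add that if the number of evaluable AP subjects differs from 16, the exact p-value decides rather than the fixed count; this matters from n = 18, where a count of 5 no longer keeps the error at or below 0.1.

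If the sponsor intends 4/16, restate the type I error as 0.21 and the power as 0.93, and present the result descriptively instead of as a claim of success.

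Either way the cost is a wording change. No subjects are added, and 5/16 still delivers the stated power of about 80%.
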